4 OUTCOMES

4.1 PRIMARY OUTCOMES:

1. **Disability:** It was measured by the Barthel Index for basic Activities of Daily Living and the Lawton index for instrumental activities of daily living.
2. **Functional status and performance-based measures:** Functional status and performance-based measures: Is measured by Short Physical Performance Battery (SPPB), Physical Activity Scale for the Elderly (PASE SCALE).
3. **Quality of Life:** Quality of life was assessed by self-reported questionnaire EuroQL 5D 5L. It will be measured during admission to hospital and follow-up.
4. **Geriatrician Intervention:** The impact of their intervention is measured by quantifying in a register any additional tests requested and medical advice by other specialists.

4.2 SECONDARY OUTCOMES:

Prevalence of Delirium: The delirium cases are detected by Confusion Assessment Method (CAM) scale.

Cognitive Impairment: Will be measured by the Mini Mental State Examination (MMSE) in the initial assessment.

Depression: will be assessed using the Geriatric Depression Scale in the baseline assessment.

Health-care associated infections: Acquired during hospitalization start.

Geriatric Syndromes: The geriatric evaluation including the following aspects: clinical, functional, mental and social.

Comorbidity: Will measured at initial assessment thorough Charlson index

Nutritional Status: Will measured at initial assessment thorough the Mini Nutritional Assessment and body Mass index.

Polypharmacy: Defined as five or more prescription drugs.

Mortality rate: Number of deaths during follow-up. It is calculated using official report of the National Statistics Institute (INE).

Average stay hospitalization: Average length of stay of stay all discharges. We will obtain from Hospital Admissions service.

Hospitalization Rate in Emergency room: Number of hospital admissions over the total of patients admitted in the hospital.

Readmission rates: Number of readmissions during of follow-up period. I will get the data in Hospital Admissions Service.

Institutionalization: Number of patients referred to nursing home after discharge or at any time during follow-up. This information is obtained directly from patients or their relatives.

Requirement of caregiver: Number of patients who require a caregiver after hospital discharge.

Caregiver burden: Will be used Zarit Scale for assessing caregiver burden

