Informal care includes different types of unpaid support which serve to compensate for the inability of subjects, usually provided by relatives or friends. This information is obtained from questionnaires applied directly to caregivers in which time spent on helping the elderly in basic Activities of Daily Living and Instrumental Activities will be specified. The time spent on these activities will be evaluated in monetary terms using 'proxy goodmethod "or" replacement method "which assesses the time spent on informal care adjusted to market prices of a professional who has to do this work (social service Careful formal).

The economic evaluation will be developed to take into account several aspects: financing health care (including only direct health costs), finance formal care (including the direct costs of health and social services) and social perspective (including all relevant costs: direct medical care + formal care (social services) and informal care.

Outcome measures:

Cost-effectiveness analysis

The cost-effectiveness analysis (CEA) is the most common test used in health economics to decide between different treatments for the same condition. In a CEA, the costs are measured in monetary units, while the benefits are measured as outcomes or in natural units. "Incremental cost-effectiveness ratio" (ICER) is estimated to show a difference in health outcomes per unit cost, after a follow-up period between intervention and usual care. The incremental cost-effectiveness is expressed by the following relation:

$$ICER = \frac{C_a - C_b}{B_a - B_b}$$

Where Ca is the cost of the intervention group and Cb is the cost of the usual care group. Ba will be health benefits in the intervention group and Bb health benefits in the usual care group, both measured in terms of change of the clinical results of the baseline.

In this study the primary outcomes will be the difference in functional status after the intervention compared with usual care group. This study will assess the cost-effectiveness of the intervention of a geriatrician compared with usual care from the perspective of society and the health care system.

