Detach the next page along the lengthwise perforation, and then tear it in half along the horizontal perforation. Use the upper half of the page (blank) for the Comprehension, Writing, and Drawing items that follow. Use the lower half of the page as a stimulus form for the Reading ("CLOSE YOUR EYES") and Drawing (intersecting pentagons) items.

COMPREHENSION

Listen carefully because I am going to ask you to do something.

Take this paper in your right hand [pause], fold it in half [pause], and put it on the floor (or table).

TAKE IN RIGHT HAND _____ 0 1
FOLD IN HALF _____ 0 1
PUT ON FLOOR (or TABLE) _____ 0 1

READING

Please read this and do what it says. [Show examinee the words on the stimulus form.]

CLOSE YOUR EYES _____ 0 1

WRITING

Please write a sentence. [If examinee does not respond, say: Write about the weather.]

0 1

Place the blank piece of paper (unfolded) in front of the examinee and provide a pen or pencil. Score 1 point if the sentence is comprehensible and contains a subject and a verb. Ignore errors in grammar or spelling.

DRAWING

Please copy this design. [Display the intersecting pentagons on the stimulus form.]

0 1

[figure not shown]
Score 1 point if the drawing consists of two 5-sided figures that intersect to form a 4-sided figure.

Assessment of level of consciousness.

Total Score =
(Sum all item scores.) _____
(30 points max.)

Alert/ Responsive	Drowsy	Stuporous	Comatose/ Unresponsive

CLOSE YOUR EYES

ANEXO 3

Patient's information obtained from his/her clinical record

(Baseline)

1. **Patient's ID:** _____
2. (Register the generic names and total daily dose of drugs that the patient has taken during the last month)

		
		

3. 3. Hospitalization

What was the main cause of hospitalization?

	Diagnosis related Code Group (GRD)	GRD description	Mean stay (days)
			

Questionnaire for the subject(baseline)

1. **Identification number** _____

2. **Level of studies completed**

- Can read and write
- Primary
- Secondary
- University
- None

3. **Is the place where you live of your property?**

- Yes
- No

4. **Number of household members where the subject lives:** _____

people

5. **Carer**

a. **Do you need a carer to assist you with your daily activities?** (for basic hygiene, to help you to move, administration of drugs, performing treatments, etc. Monitoring and supervision tasks are also included)

- Yes
- No ⇒ Skip to question #6

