b. **In the case of yes, who is your principal carer?**

- Family member ⇒ Fill in the carer questionnaire and skip to question #6
- Another non-contracted person (friend) ⇒ Fill in the carer questionnaire and skip to question #6
- Professional carer (contracted or provided by an entity)

c. **If you use the services of a professional carer,**

How many hours a week? _____ hours a week

Who pays for the service and how much?

- I pay the entire cost of _____ € per hour

(Alternative, if the subject does not know the cost per hour)

- I pay the entire cost of _____ € per month
- The cost is covered by social security or another entity
- The cost is partially covered by social security or another entity, I pay _____ € per hour

(Alternative, if the subject does not know the cost per hour)

- The cost is partially covered by social security or another entity, I pay _____ € per month

6. Hospitalisation

Have you been admitted to hospital in the last 12 months?

- Yes
- No

7. Health and social services you have required and days of service received by according to economic system during the last month and the last 6 months.

Mark the services you have required, number of days received and form of payment. In case you have required a service and have not received it, note the reason number (see the possible reasons below the table).

Kinds of services	You have needed to receive..	Days service received according to economic system			Reason for which they have not received the service (*)
		Free of charge	Direct payment	Mixed (public and private)	
During the last month...		During the last month...			
1. Telecare		— days	— days	— days	

2. Domiciliary care /help		— days	— days	— days	
3. Day centre		— days	— days	— days	
4. Occupational centre or centre for cultural, recreational and leisure activities		— days	— days	— days	
5. Other:		— days	— days	— days	
In the last 6 months...		In the last 6 months...			
6. Respite services: Temporary stays		— days	— days	— days	
7. Residential centres		— days	— days	— days	
8. Other:		— days	— days	— days	

(*) Reasons: 1 – Waiting list. 2 – Not available in the setting. 3 – Cannot pay it. 4 – Does not comply with any of the requirements. 5 – Other reasons.

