- I retired early at the age of ____ years

SOCIAL, FAMILY AND LEISURE TIME- RELATED PROBLEMS

17. Have you had any family, social o leisure time-related problem for caring the subject in the last 12 months?

- Yes
- No ⇒ Skip to question #19

18. In case of YES, please specify this(multiple choice option):

- I had to reduce my leisure time
- I have conflicts with my partner or my family
- I have no time to see or visit my friends
- I have no time to take care of myself or other people
- I have failed to start a family / I have not been able to have children (or more children)

Regarding the role played by you as PRINCIPAL CARER...

19. How much time do you invest in a normal DAY for each one of the activities?

Please specify the approximate time you spend daily on each activity

On basic hygiene and dressing or changing them	hours	minutes	a day
On bathing or showering them	hours	minutes	a day
On feeding them	hours	minutes	a day
On helping them to move around within the house	hours	minutes	a day

On cooking and preparing meals	hours	minutes	a day
Administration of drugs	hours	minutes	a day

20. How much time do you invest in a normal WEEK on each one of the following activities?

Please specify the approximate time you spend weekly on each activity

On helping them to travel outside the house	hours	minutes	a week
On helping them to contact health care suppliers	hours	minutes	a week
On helping them to organise home adaptations	hours	minutes	a week
On shopping	hours	minutes	a week
On financial, administrative or legal affairs	hours	minutes	a week
On social and leisure activities	hours	minutes	a week
Monitoring and supervision (falls)	hours	minutes	a week

Regarding the role played by OTHER CARERS (e.g. the rest of the family)

21. How much time in a normal DAY do other carers spend on each one of the following activities?

Please specify the approximate time these people spend daily on each activity

On basic hygiene and dressing or changing them	hours	minutes	a day
On bathing or showering them	hours	minutes	a day
On feeding them	hours	minutes	a day

On helping them to move around within the house	hours	minutes	a day
On cooking and preparing meals	hours	minutes	a day
Administration of drugs	hours	minutes	a day

22. How much time do other carers spend in a normal WEEK on each of the following activities?

Please specify the approximate time these people spend weekly on each activity

On helping them to travel outside the house	hours	minutes	a week

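### Question 5a, which opens the carer form at baseline, names no shopping, meals, transport or money tasks, so unpaid instrumental-care hours may be under-recorded

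*Combined protocol and SAP*

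**What the plan says.** Section 10 (Social costs, informal care) values unpaid support from time reported by carers: "time spent on helping the elderly in basic Activities of Daily Living and Instrumental Activities will be specified". That value enters the "social perspective (including all relevant costs: direct medical care + formal care (social services) and informal care". Section 4.1 makes instrumental function part of the first primary outcome, through "the Lawton index for instrumental activities of daily living".

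The time itself is collected in Annex 3. The baseline subject questionnaire asks in question 5a: "Do you need a carer to assist you with your daily activities". Its bracketed examples are: "for basic hygiene, to help you to move, administration of drugs, performing treatments, etc. Monitoring and supervision tasks are also included". A negative answer is routed "No ⇒ Skip to question #6". A positive answer goes to 5b, where the first option reads "Family member ⇒ Fill in the carer questionnaire and skip to question #6", and a non-contracted friend is routed in the same way. The carer questionnaire then times personal care and also instrumental tasks, among them cooking, shopping and "On financial, administrative or legal affairs".

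**The concern.** The costing plan is wider than the examples in the question that admits carers to it. Question 5a asks whether the patient needs a carer and illustrates this mainly with personal care. A patient who manages washing, moving and medicines, but whose daughter does the shopping, cooking and banking because the patient no longer can, may reasonably answer No. No informal hours are then recorded for that patient at baseline, although section 10 intends to cost them.

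The trial population makes this plausible. Patients are frail, older than 75 and not nursing-home residents, and they are excluded for physical disability only when the Barthel score is below 40. People who are independent in basic care but need help with instrumental tasks are therefore eligible. At stake is the informal-care component of the societal analysis, which is a secondary economic outcome. Section 10 also expects probit or ordered probit models for informal care cost. If these model any care against none, the answer to 5a largely fixes the dependent variable. Hours that were never collected cannot be recovered at analysis.

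**Working it through.** The plan gives no figure on this point, so the check is of routing and coverage, followed by what would be needed to size the effect.

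**1. Routing on the baseline subject form**

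| Answer | Next step | Carer form completed? |
|---|---|---|
| 5a No | Question 6 | No |
| 5a Yes, 5b family member | Carer form | Yes |
| 5a Yes, 5b other unpaid person | Carer form | Yes |
| 5a Yes, 5b professional | 5c (hours, payment) | No instruction |

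Item 5b is the only item on the subject form that leads to the carer form, and a No to 5a bypasses it.

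**2. Activities timed against activities named**

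Question 19 times 6 daily activities and question 20 times 7 weekly ones: 6 + 7 = 13.
- Named or clearly covered in 5a: hygiene and dressing, bathing, moving within the house, drugs, and supervision. That is 5, or 6 if help to move is read to include travel outside.
- Not named: feeding, cooking, contact with health care suppliers, home adaptations, shopping, finances, and social and leisure activities. That is 13 − 6 = 7, or 13 − 5 = 8 with travel outside.

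Of the 8 Lawton items, 5a names 1 (medication), or 2 if moving includes transport.

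**3. Follow-up**

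The week-12 and week-52 carer forms tell a carer new to the study to complete the baseline carer form, either because the patient previously had no need of a carer or because the carer has changed. This reopens the route but rests on the same notion of needing a carer. Annex 3 shows a subject questionnaire only for baseline, while Table 2 marks the economic evaluation at discharge, 3 months and 12 months. How carers are identified at those visits is not defined.

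**4. Size**

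Let f be the share of all patients who need only unnamed tasks and answer No, and h their mean unpaid hours per week. Missed hours per randomised patient per week = f × h. The documents give neither value. As assumptions only:
- f = 0: 0 hours, whatever h is.
- f = 0.10, h = 2: 0.10 × 2 = 0.2 hours.
- f = 0.30, h = 8: 0.30 × 8 = 2.4 hours.

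At an assumed EUR 12 per hour, the last two are 0.2 × 12 = EUR 2.40 and 2.4 × 12 = EUR 28.80 per week. Multiplying by 52 would assume that a baseline No keeps the carer out for a year, which the documents do not say.

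**5. Direction**

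The baseline form is completed for both arms under the same rule, so a between-arm effect would have to come through follow-up. Suppose that the 5a wording decides entry there too. Let h be weekly instrumental hours and b weekly basic-care hours.
- A control patient needs h only and an intervention patient needs nothing. The true saving is h and the recorded saving is 0 − 0 = 0, so the saving is missed.
- A control patient needs b + h and an intervention patient needs h only. The true saving is (b + h) − h = b. The recorded saving is (b + h) − 0 = b + h, so it is overstated by h.

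The error can go either way.

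**The case against.** The strongest reply is that 5a is already broad. Its stem concerns daily activities without limit, and its list is open-ended. It names drug administration, which is Lawton item G. It also omits feeding, a basic activity that the carer form times, so the list is plainly illustrative. The carer form defines the principal informal carer by the patient's limited autonomy and by time or responsibility, not by basic care. All of this stands. A reader might infer that the carer form is open only to patients needing basic care; the text contradicts that.

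A reader might also infer that instrumental help is never timed. That is not supported either. Any Yes with an unpaid principal carer leads to timing of cooking, shopping and finances, and the follow-up forms allow later entry. Section 9.1 lists the caregiver among baseline demographics. Sections 9.2 to 9.4 call for caregiver burden with the economic questionnaires, with no stated dependence on 5a.

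Two further inferences fail: that the societal cost difference is biased toward no effect, and that a definite sum per patient is lost. The direction can reverse, and every input to such a sum would be assumed.

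What the reply does not remove is the dependence on how each patient reads the question. Nothing in the documents ensures that patients in three countries will read a list of personal-care examples as covering shopping or banking.

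**Conclusion.** The point holds as a risk of under-recording. Question 5a decides entry to the carer form at baseline, and its examples omit most of the instrumental activities that section 10 undertakes to time. A patient with instrumental need only may be routed past that form, and the follow-up entry note does not clearly repair this.

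The shortfall is f × h, with both terms unknown. It is zero if every such patient reads the stem broadly. Neither the size nor the sign of the effect on the between-arm societal cost can be derived from the documents. The conclusion rests on the Annex 3 skip rules being followed as printed, and on some patients taking the examples as a guide to what counts. It concerns one component of a secondary economic outcome, not the Lawton measurement itself. It still merits correction before data collection because the remedy is cheap.

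**What to change.** Keep the need-based stem of 5a and add instrumental tasks to its examples, for instance: *shopping, preparing meals, transport outside the home, managing money or paperwork, because of your health*. Ask the same question at 3 and 12 months, and use the answer to decide who completes the carer form. Record whether the need is basic, instrumental or both, so that informal cost can be analysed by type.

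Two alternatives should be avoided. Asking simply whether anyone helps would count ordinary household sharing, such as a spouse who has always cooked, whereas section 10 treats informal care as compensating for the patient's inability. Tying the caregiver item to basic care would narrow the section 4.2 outcome on requirement of a caregiver, which has no such limit.

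The cost is a longer example list, one added type-of-need item, the question repeated at two follow-up calls, and somewhat more carer forms to complete. The change does not by itself cover housekeeping, laundry or telephone use, which are Lawton items with no timing line on the carer form.

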10 ECONOMIC EVALUATION

An economical evaluation of the program will be conducted to detect and handle the frail elderly in different health areas. We will conduct a comparative analysis in terms of costs and benefits of a geriatrician's intervention compared with usual care.

Information on both patients and caregivers about health resources and social services use and time spent by the caregiver will be collected. The next step is to translate this resource consumption in monetary terms. The costs will be reported in euros and in places where it is not used this coin the current exchange will take place.

The total cost is the sum of three different types of costs: directly deriveate from care; formal care costs (professional) and informal care costs (family and friends)

Direct health care costs:

These costs are related to inpatient treatment, outpatient treatment, medicines, etc. These are estimated from the use of health services by assigning a monetary value for each resource used.

Health resources will be identified and measured through questionnaires. Each center will give us the price or the monetary value of each resource. If some of this information is not available, it will be obtained from a systematic review of studies of cost of illness for each country.

Formal care costs (Social Services):

Formal care includes those generated by social services which can be public or privately funded institutions such as day care centers, remote assistance, scheduled home care, etc. These costs will be identified, measured and evaluated through questionnaires. Ideally, members of each research team from each center must provide to the economic team price and monetary values (unit costs) of resources for social services.

If data about unit cost of social services are not available, a review of the literature will be performed to obtain the data by country.

Social costs (informal care)

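### Question 5 of the Annex 3 subject questionnaire routes by principal carer, so a patient with both paid and unpaid care cannot be fully costed for the societal perspective

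*Combined protocol and SAP*

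**What the plan says.** Section 10 states: "The total cost is the sum of three different types of costs", namely direct care, formal (professional) care and informal care by family and friends. The societal perspective adds all three, and the formal and informal parts are to be measured by questionnaire.

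The subject questionnaire in Annex 3 is headed baseline. Question 5b asks who the principal carer is and offers three answers:

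- A relative, printed as "Family member ⇒ Fill in the carer questionnaire and skip to question #6".
- An unpaid friend, which carries the same two instructions as the answer for a relative.
- A paid carer, printed as "Professional carer (contracted or provided by an entity", which has no routing instruction, so the patient goes on to 5c.

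Question 5c opens with "If you use the services of a professional carer" and asks for weekly hours, payer and price. Question 7 lists services, among them "2. Domiciliary care /help", under the column heading "Days service received according to economic system".

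Unpaid time is asked only in the carer questionnaires, including a block headed "Regarding the role played by OTHER CARERS (e.g. the rest of the family". Sections 9.2 to 9.4 and Table 2 schedule the economic evaluation at discharge, 3 months and 12 months, and those sections refer to Index 3 for it. Annex 3 contains carer questionnaires for weeks 12 and 52, but no subject questionnaire beyond baseline.

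**The concern.** A patient may have a daughter who does most of the caring and a paid helper who comes each morning, or the reverse. Section 10 needs both amounts for that patient. The routing at 5b leads to the detailed record of one or the other, depending on who is named as principal. The opening words of 5c cover anyone who uses a professional carer, yet the jump at 5b lets only patients with a professional principal carer reach it. That contradiction looks like an oversight.

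At stake are the cost-effectiveness analysis from society's perspective and the planned models of formal and informal care cost, both of which use these hours. Hours that were never asked for cannot be recovered in the analysis.

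**Working it through.** The plan gives no figure to reproduce: it states no care hours, no unit costs and no share of patients with mixed care. The check is therefore a trace of the routes, followed by an illustration on assumed values.

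**1. Routes for a patient who needs a carer (Annex 3, subject questionnaire)**

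| Answer to 5b | 5c: professional hours and price | Carer questionnaire: unpaid hours | Question 7: service days by payer |
|---|---|---|---|
| Family member | bypassed | instructed | reached |
| Friend | bypassed | instructed | reached |
| Professional | reached | no instruction | reached |

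No row leads, as written, to both professional hours and unpaid hours.

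**2. What question 7 recovers.** It counts days in the last month (home help, telecare, day centre) or the last six months (respite, residential care) by payment type. These are close to the services that section 10 lists as formal care, and days can be priced with centre or literature unit costs. It asks neither hours nor price, so a one-hour visit and a full day count alike. It asks nothing about unpaid time, so on the professional route this form has no substitute source.

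**3. Follow-up.** I take Index 3 in section 9 to mean Annex 3. Either the baseline subject questionnaire is reused at the scheduled economic contacts, and the skip applies after randomisation; or it is not, and no form shown collects professional hours or service days at follow-up. Discharge destination and current residence are recorded, but neither gives hours or days.

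**4. Illustration (all values assumed, none from the documents).** Let P be professional hours per week, F unpaid hours per week, and q the fraction of P that question 7 recovers. Take P from 5 to 20 and F from 20 to 40.

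- Family or friend principal: omitted share = P(1 − q)/(P + F).
  - q = 0: 5/45 = 11% to 20/40 = 50%
  - q = 0.5: 2.5/45 = 6% to 10/40 = 25%
  - q = 1: 0%
- Professional principal, no carer questionnaire completed: omitted share = F/(P + F), from 20/40 = 50% to 40/45 = 89%. Question 7 does not change this.

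**5. Cost difference.** Section 10 uses Ca − Cb. Its error is the difference between arms in mean omitted cost. That is zero if the arms omit equally, and may take either sign if they do not.

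**The case against.** The strongest reply is that the gated form is a baseline form. Table 2 marks the economic evaluation at discharge, 3 and 12 months, not at the initial visit. The week-12 and week-52 carer questionnaires have no gate like 5b: the principal informal carer completes them, and a carer new to the study completes the baseline version. This stands, and it means that unpaid hours are not shown to be suppressed at follow-up. It does not cover the professional side, because no follow-up form shown asks for paid hours or service days. The note on new carers also does not clearly reach a relative passed over at baseline because a professional was principal.

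Second, the carer questionnaire is addressed to the principal informal carer and does not exclude patients who also have paid help. That is correct: the professional route is silent rather than prohibitive. Unpaid hours may therefore go unrecorded, depending on what each site does; they are not certain to be lost.

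Third, question 7 limits the loss on the family and friend routes. A reader might infer that mixed-care patients cannot be costed at all; the documents do not support that, because service days can be priced.

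A reader might also infer a bias between arms, on the reasoning that a geriatric team arranging home help changes who is called principal and so creates a false saving. The documents do not support this either. The label is shown only at baseline, where randomisation balances it in expectation, and reuse of the form after randomisation is not established. Any figure for such a saving would rest wholly on assumed hours and an assumed shift in labels. Equal paid and unpaid hours are also not the only case without bias: matching omissions in the two arms give none either.

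**Conclusion.** The routing defect is real and limited. As written, the subject questionnaire does not lead to professional hours and unpaid hours for the same patient, while section 10 needs both. An omission can only lower that patient's recorded total, so mixed-care patients cannot be fully costed. The amount cannot be derived from the documents, and the direction of any effect on the cost difference between arms is undetermined. The percentages above show only how much depends on the assumed mix of care and on how well question 7 substitutes.

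The professional route is the weaker of the two, since it has no fallback on that form. The follow-up position has to be settled in either case, because both readings leave a gap. The consequence is confined to the secondary economic objectives; the clinical outcomes are not touched. The conclusion assumes that sites follow the routing literally and that Annex 3 contains all the economic forms.

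**What to change.** 1. In 5b, remove the jump to question 6 from the family and friend answers.
2. Ask 5c of every patient who uses any professional carer, principal or not.
3. State that the carer questionnaire is given whenever any unpaid carer exists, whoever is principal.
4. Use the corrected question 5 and question 7 at each scheduled economic contact (discharge, 3 months, 12 months), and add the follow-up subject form to Annex 3.
5. In section 10, state that formal and informal cost are summed per patient, and that home care reported in both 5c and question 7 is counted once.

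The cost is a routing edit in the eCRF and on paper, a few more minutes for each patient with mixed care, and the time to administer questions 5 and 7 at follow-up if that is not already intended.
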